6.2.2 Enrollment, Baseline, and/or Randomization

Enrollment & Randomization

Enrollment begins when the participant signs the informed consent form for the 3-session experiment, at the start of the first lab session (i.e., baseline/orientation day).

-
-

After successful screening, participants will be randomized to either the AM-session-first condition or to the PM-session-first condition using the AM/PM Randomization REDCap database. Just prior to the baseline session, the participant will be assigned to a cognitive task condition using the Task Condition Randomization REDCap database. Finally, just before the first tDCS session, the participant will be assigned to a Soterix stimulation code, and to an electrode placement (either PFC or parietal), using the Participation REDCap database.

Baseline Assessments

During baseline assessment participants will complete cognitive tasks, demographic information, and other forms (Table 6.1).

[Morningness-Eveningness Questionnaire](#) (MEQ) *online survey* - Participants will take the MEQ, assessing AM and PM testing preferences, which is correlated with physiological measures of circadian rhythms and predicts time-of-day effects on cognitive tasks in younger and older adults (Horne & Ostberg, 1976; see May & Hasher, 2017). Younger adults are expected to express at least a mild preference for PM testing (approximately 70% of younger adults in our prior sample), and older adults at least a mild preference for AM testing (typically 75% of older adults, see Yoon et al., 1999). (See Appendix).

[Actigraphy and Sleep Diary](#) *online survey* - During the initial orientation session participants will be equipped with an actigraphy watch and instructions for this and the sleep diary, and these data will be collected over a minimum 7-day period. During this period, participants will return to the lab for 2 testing sessions (AM/PM, nonconsecutively), returning the actigraphy watch and sleep diary on the final testing session. These measures will be used to help interpret the differential time of day effects (AM vs PM) on cognitive functions that we predict in younger and older adults, as well as the predicted interaction with tDCS brain stimulation.

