9 STATISTICAL CONSIDERATIONS

9.1 General Design Issues

Overall design (from Precis section): 50 Younger Adults will be randomly assigned to three between-subjects tDCS conditions (left prefrontal, sham, left parietal control, total YA n=150) and 50 cognitively normal older adults will be randomly assigned to two between-subject tDCS conditions (left prefrontal, sham, total OA n=100). Each participant will complete 3 sessions: orientation/baseline (no tDCS, time varies), AM tDCS, PM tDCS (counterbalancing the order of the AM and PM sessions). Primary outcome measures will be cognitive task performance (episodic recollection accuracy primary, working memory accuracy secondary) as a function of 3 key factors (age group, tDCS condition, and time-of-day) and their interaction,

-
-

and also as a function of secondary factors obtained from actigraphy sleep data, sleep diary/log data, and the Morningness-Eveningness Questionnaire (aka the Owl-Lark assessment).

Rationale for within-subjects AM and PM testing: Each participant will take both an AM and a PM testing session. Within-subjects designs are generally preferred over between-subject designs, because they reduce the impact of individual variability on performance that is unrelated to the AM/PM manipulation, thereby increasing the likelihood of detecting AM/PM effects. However, within-subject designs introduce the possibility of practice effects across sessions, but we will control for such order effects by counterbalancing the order of the AM and PM sessions across participants in each arm. Moreover, collecting a no-tDCS cognitive baseline for all participants (during the first session) will give all participants familiarity and practice with the cognitive tasks, thereby reducing the impact of such practice effects on the subsequent AM and PM tDCS/sham testing sessions.

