10 DATA COLLECTION AND QUALITY ASSURANCE

10.1 Data Collection Forms

Information will be collected for each participant by the Study Coordinator, or a research assistant under their immediate supervision. For double-blinding, no member of the PI's research team that will interact with participants will know the stimulation codes that differentiate active vs. sham tDCS. The PI will generate this code list before the study is initiated, and then share it with the DSMB. The PI will not refer back to this code list until data collection is ended, and the PI will not administer study procedures to study participants. The research team will share de-identified data with the PI during the study, to troubleshoot or as needed, but no analysis of tDCS vs sham will be conducted until the end of the study.

Maintaining confidentiality of participant records will be achieved by storing these records in

-
-

password protected excel files on a lab computer, backed-up on the University's protected server, and also on external hard-drive in the lab by the Study Coordinator.

1. Qualtrics Survey - *Adverse events*
 - Contains information about any Adverse Events (both serious and non-serious). Data from this survey will be used to generate routine updates to the DSMB regarding adverse events. The survey is modeled off of the NIA templates for adverse event and serious adverse event logs.
2. REDCap DB - *AM/PM Randomization DB*
 - Enables participant assignment to the AM-session-first or PM-session-first condition, prior to the participant's baseline session.
3. REDCap DB - *Task Condition Randomization DB*
 - Enables participant assignment to one of 12 task varieties, during the participant's baseline session.
4. REDCap DB - *Participation DB*
 - Enables participant assignment to active or sham stimulation, and, if the participant is a younger adult, to either the dlPFC or parietal electrode placement. Will also contain information about each of the participant's visits.
5. Spreadsheet - *OA Contact Log*
 - Contains information about older adults who have been contacted about participating in the study.
6. Spreadsheet - *Screening Log*
 - Contains information about participant eligibility based off the Inclusion/Exclusion Criteria Screening Survey.
7. Paper log - *Payment Log*
 - Contains the subject's name and a place to sign to indicate payment was received.
8. Spreadsheet - *Blinding Key*

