## Analysis Plan

### PRIMARY ANALYSES

Set 1 (1a, 1b, 1c). The first set of primary analyses will estimate the effect of tDCS to left dlPFC on cognitive performance and the extent to which different aspects of the cognitive task will be impacted. These analyses will be done separately for episodic and working memory.

1.a This analysis will be done on younger adults only. We shall use a linear mixed (i.e., random participant-level intercepts) model with memory performance (defined as memory accuracy computed by subtracting false alarms from target hits) as the dependent variable and stimulation condition (stimulation vs. sham), session Time of Day (AM, PM), and task manipulations (stimulus format and difficulty) as within-subjects predictors along with session order as a covariate (session 1, session 2). Interaction terms between stimulation condition and both task manipulation and time of day will be used to examine the impact of these variables on the stimulation effect.

1.b This analysis will use the same model as in 1a (above), but including data from both younger and older adults and a corresponding age-group factor in the model. Interaction terms between age group, stimulation condition, and time-of-day will be used to determine whether the overall stimulation effect is the same for older as for younger adults, and if not, whether the difference varies by time of day.

1.c This analysis will assess the impact of preferred time of day on tDCS effects, using wrist-worn (minimum 7-days, max 12-days) accelerometry to measure preferred time of day (i.e. “Owl” vs “Lark”), and validation using the subjective Morningness-Eveningness Questionnaire (MEQ). For this analysis, accelerometry-derived variables capturing preferred time of days (eg, including wake time, rise time and midpoint of sleep) will be added as covariates to the model in 1.b., and interactions between these, time of day and stimulation effects will be evaluated.

Set 2. The second set of primary analyses will focus on dlPFC vs parietal vs sham effects in younger adults only. For these analyses, similar models to those described above will be used (e.g., 1a, 1c, 2), except we will include 3 levels for tDCS (dlPFC, parietal, sham). We will test the relative fit of three models: (1) a model in which parietal has the same effect as sham, (2) a model in which parietal has the same effect as dlPFC, and (3) a model in which the effect of parietal differs from the other two conditions.

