All analyses will initially be performed without using the baseline performance measures. We shall then repeat each analysis adjusting for the baseline value of the cognitive measure being analyzed. To the extent that the cognitive measures are highly correlated across timepoints, the latter analyses will provide additional power.

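### No SAP model includes the 12-level task variety to which participants are randomised, so any stable difficulty difference between varieties stays in the error of the stimulation test: a possible loss of precision, not bias

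*SAP*

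**What the plan says.** Protocol 6.2.2 says that around the baseline session "the participant will be assigned to a cognitive task condition using the Task Condition Randomization REDCap database". Protocol 10.1 describes what that database does: "Enables participant assignment to one of 12 task varieties". The stimulation code is drawn later, just before the first tDCS session, from a different database. No section says that the stimulation draw is balanced on variety.

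The SAP's model 1.a is introduced as follows: "We shall use a linear mixed (i.e., random participant-level intercepts) model with memory performance". Besides stimulation and time of day, it lists "task manipulations (stimulus format and difficulty) as within-subjects predictors along with session order as a covariate (session 1, session 2"). Model 1.b inherits this: "This analysis will use the same model as in 1a (above), but including data from both younger and older adults". Model 1.c adds accelerometry variables, and Set 2 adds a third stimulation level. The last step of the primary analyses is a repeat with one more covariate: "We shall then repeat each analysis adjusting for the baseline value of the cognitive measure being analyzed". Task variety appears in none of these, and no reason is given.

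The documents do not say what distinguishes the 12 varieties, whether they differ in difficulty, or whether a variety fixes which form is used in which session.

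**The concern.** Task variety is a randomised design factor that is already recorded. The SAP adjusts for session order, which Protocol 9.1 controls by "counterbalancing the order of the AM and PM sessions across participants in each arm", but not for this second task-design factor.

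Each participant has the same stimulation condition in both sessions (Protocol 9.1), so the stimulation effect is a between-participant comparison. If some varieties are consistently harder, that spread goes into the variance against which stimulation is judged. Protocol 9.1 itself expects this comparison to be limited by individual variability, and the planned 50 per group gives almost exactly 80% power with nothing to spare. At stake is some avoidable loss of precision.

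**Working it through.** **Inputs from Protocol section 9 (sample size).** Difference .12, SD .21 (d = .12/.21 = .571), 50 per group, two-sided alpha .05, AM-PM correlation .25.

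**The plan's own figure.** Normal approximation: n = 2 x (1.960 + 0.842)^2 / .571^2 = 48.1, so 49 per group. The noncentral t gives 50, with 80.8% power at n = 50 (80.6% for d = .57). The stated 50 reproduces.

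**Reference power without variety (normal approximation).**
- One-session stimulation contrast: z = .571/sqrt(2/50) = 2.86, power 81.5%.
- Stimulation x time of day, for a .12 effect present in the AM only: z = .571/sqrt(4 x .75/50) = 2.33, power 64.5%.

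**Which tests can be affected.** Write a participant's two scores as participant effect + variety effect + session error. If the variety effect is the same in both sessions, it cancels from AM minus PM but stays in the AM-PM average. A simulation of 50 v 50 (3,000 replicates) with variety variance added as a share of .21^2 shows the consequence:

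| Added share | Constant variety effect: SE stimulation | Constant: SE stim x time | Session-specific forms: SE stimulation | Session-specific: SE stim x time | Session-specific: power, stim x time |
|---|---|---|---|---|---|
| 0% | .0331 | .0514 | .0331 | .0514 | 65% |
| 5% | .0344 | .0512 | .0336 | .0528 | 62% |
| 10% | .0355 | .0514 | .0343 | .0543 | 60% |
| 20% | .0377 | .0513 | .0355 | .0572 | 54% |

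With a constant effect, the interaction SE does not move beyond simulation error. It rises only when forms differ by session.

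**What modelling variety would recover.** The between-variety SD s is not in the documents. Assume s = .03, .05 or .08, already contained in the SD of .21.
- Share of single-session variance, s^2/.21^2: 2.0%, 5.7%, 14.5%.
- Share of within-person variance, s^2/(.75 x .21^2): 2.7%, 7.6%, 19.3%.

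The SE with a random variety effect comes from generalised least squares, Var = (X'V^-1 X)^-1. For one session, V = s^2 ZZ' + (.21^2 - s^2)I, where Z marks the 12 varieties. For AM minus PM with session-specific forms, V = 2s^2 WW' + 2(.75 x .21^2 - s^2)I, where W is Z with its sign set by session order. Varieties are spread at random over 50 v 50, and the variance components are treated as known, which is the best case.

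| s | One-session power (81.5% without variety) | Stim x time power, session-specific forms (64.5% without variety) |
|---|---|---|
| .03 | 81.7% | about 64 to 65% |
| .05 | 82.3% | about 66% |
| .08 | 84.9% | about 70 to 71% |

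The gains are about 0, 1 and 3 points for one session, and 0, 1 and 5 to 6 points for the interaction.

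**Random or fixed.** A fixed 12-level factor uses 11 df. Under chance imbalance it also loses about 11/99 of the information on stimulation. Noncentral-t power with d/sqrt(1-v) x sqrt(1-11/99) and 87 df is 75.9%, 78.0%, 80.2% and 84.6% for v = 0, 5%, 10% and 20%, against 80.8% unadjusted. So it loses power until varieties carry more than about 10% of the variance. In a simulation with no variety variance (1,500 replicates), one-session power was 82.3% unadjusted, 82.4% with a random effect and 77.2% with a fixed factor. Rejection rates under the null were 4.7% to 6.7% with the random effect and 4.5% to 5.9% without it, hence the degrees-of-freedom correction below.

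**The case against.** The strongest reply is that leaving a form factor out of a randomised comparison is legitimate. Both assignments are random, so the estimates are unbiased in expectation and the usual standard errors already cover chance differences in variety mix between arms. That stands. A reader might infer from arms of 50 not dividing by 12 that a harmful imbalance is left uncorrected. The arithmetic does not show this: an even allocation would put 4 or 5 participants of each variety in an arm, and the documents do not say how the two randomisations relate.

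A reader might also infer that any difficulty difference adds noise to the time-of-day tests. The participant intercept rules that out for a constant variety effect. Only forms that change by session would reach those tests, and no passage describes that.

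A third tempting step is to scale the SE by sqrt(1 - share), as if modelling removed all variety variance. For s = .08 that gives 87.1% for one session and 73.8% for the interaction. With about 100 participants over 12 varieties spread at random over arms, the recovery is smaller, as tabulated above.

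Finally, the baseline-adjusted repeat may absorb part of a constant variety effect. That is true, but it is the second analysis; the initial one uses no baseline data, and how much baseline carries is unknown. What remains is an unexplained omission of a randomised factor from the models.

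**Conclusion.** The point holds as a possible loss of precision. Variety is randomised and recorded, it is in no SAP model, and any stable difference between varieties stays in the between-participant error of the stimulation test. An effect on AM-PM contrasts or on stimulation x time of day is conditional on session-specific forms, which the documents neither state nor exclude. There is no bias and no threat to the validity of the tests.

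The size is modest and rests on assumption. For between-variety SDs of .03 to .08, the best-case gain is about 0 to 3 power points for the one-session contrast and 0 to 6 points for the interaction in the conditional case. It is nil if the varieties are equivalent. These figures use one summary score per session and 50 v 50, not the full model with format and difficulty cells. The case for change is that the remedy is cheap and, with a random effect, showed no measurable power loss when varieties do not differ.

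**What to change.** Before the stimulation codes are broken (Protocol 9.2.1), amend the SAP to:

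1. State what the 12 varieties are and whether a variety determines which form is used in each session.
2. Add a random intercept for task variety to models 1.a, 1.b, 1.c and Set 2, and to their baseline-adjusted repeats. If forms differ by session, add a random intercept for variety x session.
3. Use a small-sample degrees-of-freedom correction (for example Kenward-Roger or Satterthwaite), and do not enter variety as an 11-df fixed factor.
4. Say in advance what happens if the variety variance is estimated as zero: the term contributes nothing and the result is reported as such.

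If the team prefers to leave variety out, one sentence of justification would close the point. The cost is SAP wording, one variable that the REDCap assignment already produces, slightly more model complexity, and a possible zero variance estimate. Settling it while blinded also removes a later discretionary choice.

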50 Younger Adults will be randomly assigned to three between-subjects tDCS conditions (left prefrontal, sham, left parietal control, total YA n=150) and 50 cognitively normal older adults will be randomly assigned to two between-subject tDCS conditions (left prefrontal, sham, total OA n=100). Each participant will complete 3 sessions: orientation/baseline (no tDCS, time varies), AM tDCS, PM tDCS (counterbalancing the order of the AM and PM sessions). Primary outcome measures will be cognitive task performance (episodic recollection accuracy primary, working memory accuracy secondary) as a function of 3 key factors (age group, tDCS

○

○

condition, and time-of-day) and their interaction, and also as a function of secondary factors obtained from actigraphy sleep data, sleep diary/log data, and the Morningness-Eveningness Questionnaire (aka the Owl-Lark assessment).

Interventions and Duration

Morning testing sessions will be scheduled at 8 or 9 AM, afternoon testing sessions will be scheduled at 3 or 4 PM. These times were chosen to be similar to those we used in our preliminary work that demonstrated time-of-day effects on tDCS in younger adults (9 am vs 1 pm), except we have shifted the PM session to 3 or 4 PM to be more consistent with aging studies that have found AM and PM effects on episodic memory (May & Hasher, 2017; May et al., 1993; Intons-Peterson et al., 1998)

Active tDCS will involve 20 minutes of continuous electrical stimulation (2.0 milliamperes, mA). Sham tDCS will involve 1 minute of stimulation at the start of the 20 minute period (i.e., 30 s to gradually ramp up to 2.0 mA, and then 30 s to ramp down), and also 1 minute of stimulation at the end of the 20-minute period. As in our prior work, during stimulation participants are instructed to sit quietly while remaining awake in preparation for the upcoming memory test, but no further instructions are given.

Standard Anodal Procedure. The tDCS technique that we use, modeled after the most effective techniques found in the literature (e.g., Nitsche et al., 2008), and aimed at targeting left

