6.2.3 Follow-up Visits (AM and PM Visits)

All participants will be enrolled in the baseline/orientation session, and they then will be assigned to active (or sham) tDCS for two follow-up experimental sessions, one in the AM and one in the PM.

- The time between each session will be at least 48 hours (i.e., at least 1 day intervening), thereby ensuring at least 1 full day of actigraphy data collected outside the lab prior to each tDCS session.
- The time between the baseline/orientation session and the final tDCS testing session should be no less than 7 days and no more than 12 days, thereby obtaining at least 7 days of actigraphy data and also providing some flexibility in the scheduling of the final session.

Follow up Assessments

Measures will include cognitive tasks, actigraphy, and the questionnaires listed in table 6.1.

-
-

Substance Use Survey See description above.

Arousal Rating *online survey* - Participants are asked about their alertness level before the encoding portion of the cognitive task adn before and after tDCS stimulation.

Post-tDCS Application Survey *online survey* - Participants report sensations during tDCS stimulation as well as what was on their mind during the stimulation.

Cognitive Tasks *computerized tasks* - See description above.

Adverse Events Questioning *verbal report* - Participants are asked if they have experience any after the baseline session. Responses are recorded in the Adverse Events Survey (see List of Administrative Logs).

6.2.4 Completion/Final Evaluation The final experimental session will be the final evaluation, and at the end of this session participants will complete a Post-Experiment Survey and finally receive a debriefing.

Post-Experiment Survey *online survey* - Participants report their sensations during the tDCS procedure, their expectations as to whether and how tDCS impacted performance, and also whether and how they believed they performed during the AM and the PM testing sessions.

Debrief Sheet *paper info sheet* - Participants are given an information sheet about the purpose of the study, which includes information about the stimulation and sham conditions (but not their own assignment), as well as hypotheses for AM and PM testing.

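### The SAP 1.c chronotype moderator includes nights after stimulation has begun and the night before the AM visit, while the pre-stimulation MEQ serves only as validation

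*SAP*

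**What the plan says.** SAP 1.c, listed under Primary Analyses, examines whether preferred time of day changes the tDCS effect, "using wrist-worn (minimum 7-days, max 12-days) accelerometry to measure preferred time of day". The derived variables, "including wake time, rise time and midpoint of sleep) will be added as covariates to the model in 1.b", are then tested for interaction with time of day and stimulation. The list of variables is given by example, and no rule selects nights. In 1.c the questionnaire's role is "validation using the subjective Morningness-Eveningness Questionnaire (MEQ").

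Protocol 6.2.2 fixes the recording period: "During the initial orientation session participants will be equipped with an actigraphy watch", and they wear it until the last visit, "returning the actigraphy watch and sleep diary on the final testing session". Both tDCS visits fall inside that period. Protocol 6.2.3 puts the final visit 7 to 12 days after baseline and adds "The time between each session will be at least 48 hours". Under Interventions and Duration, "Morning testing sessions will be scheduled at 8 or 9 AM".

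The MEQ belongs to the baseline assessments in Protocol 6.2.2: "Participants will take the MEQ, assessing AM and PM testing preferences". The stimulation code is assigned later, just before the first tDCS session. Protocol 9.1 names the MEQ as a secondary factor in its own right, beside actigraphy and the sleep diary.

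**The concern.** A test of effect modification in a randomised trial is clean when the modifier was fixed before assignment, because randomisation then balances the arms at each level of it. A modifier measured partly after assignment loses that protection. If stimulation altered sleep timing, participants with the same recorded midpoint in the active and sham arms would no longer be comparable, and an interaction between chronotype, time of day and stimulation could partly reflect that change.

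The night before the AM visit is a separate and smaller matter. On that night an appointment may set wake time in place of preference, which would make late risers look more like early risers. Protocol 6.2.2 expects about 70% of younger adults to prefer PM testing and about 75% of older adults to prefer AM testing, so any distortion would plausibly fall more on the younger group.

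What is at stake is the interpretation of one moderator analysis. The main comparison of stimulation with sham is not affected.

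**Working it through.** Neither document gives a figure for the share of nights that follow stimulation, so there is none to reproduce. The share follows from the visit rules.

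**Inputs.** Recording starts on day 0 and ends at the final visit (Protocol 6.2.2). The final visit is on day L = 7 to 12, with at least one day between sessions (Protocol 6.2.3). The first tDCS session is therefore on day f = 2 to L − 2. Neither document fixes f.

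**Step 1: nights after first stimulation.** If the whole record is used, the share is (L − f)/L.

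| L | f | Nights after first tDCS | Share |
|---|---|---|---|
| 7 | 2 to 5 | 5 to 2 | 71% to 29% |
| 8 | 2 to 6 | 6 to 2 | 75% to 25% |
| 9 | 2 to 7 | 7 to 2 | 78% to 22% |
| 10 | 2 to 8 | 8 to 2 | 80% to 20% |
| 11 | 2 to 9 | 9 to 2 | 82% to 18% |
| 12 | 2 to 10 | 10 to 2 | 83% to 17% |

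That gives 4 + 5 + 6 + 7 + 8 + 9 = 39 schedules. Most nights follow stimulation in 18, exactly half in 3, and a minority in 18. If all are equally likely (assumption), the mean share is 50%. Reading 48 hours strictly gives a mean of about 45% for AM-first participants (assuming a baseline visit later in the day than the AM slot) and 55% for PM-first.

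**Step 2: can the 7-day minimum be met before stimulation?** Seven earlier nights need f of at least 7, and L − 2 ≥ 7 gives L ≥ 9. On a 7- or 8-day schedule it cannot be met. On the 7-day schedule the minimum uses every night.

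**Step 3: the night before the AM visit.** It is 1/12 = 8% to 1/7 = 14% of nights. If wake time that morning is x hours early (assumption), mean wake time moves by 60x/L minutes:

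| x | L = 7 | L = 12 |
|---|---|---|
| 0.5 h | 4 min | 2.5 min |
| 2 h | 17 min | 10 min |
| 3 h | 26 min | 15 min |

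Sleep midpoint moves about half as much if bedtime is unchanged.

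**Step 4: what that does to the moderator.** An illustrative simulation assumed a mean habitual wake time of 7.0 or 8.5 h, a between-person SD of 1.0 or 1.25 h respectively, a night-to-night SD of 1 h, and wake time on the visit morning no later than 7:00 or 7:30. The slope of measured on true habitual wake time fell from about 1.00 to between 0.88 and 0.97, a compression of 3% to 12%. The correlation with true wake time fell by at most about 0.005. With only two nights that correlation was 0.82 to 0.87, against 0.94 to 0.97 for the full record.

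**The case against.** The strongest reply is that the harm is small or unproven. The protocol describes cognitive effects lasting at least 25 to 30 minutes after stimulation and adverse events that are mild and transient. Nothing in it suggests that a 20-minute session shifts wake times over several days. Objective actigraphy is also a legitimate first choice for measuring sleep timing. All of this stands, and it limits the size of the point. It does not make the moderator a pre-treatment variable.

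A reader might infer four stronger things that the documents do not support:

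- That chronotype is measured mostly after stimulation. The share runs from 17% to 83%, and the allowed schedules split evenly.
- That the AM visit cuts everyone's sleep short. No wake times are given, and an habitual early riser may lose nothing.
- That the AM wake-up could create a false stimulation interaction. Every completer has one AM visit, stimulation is randomised, and session order is counterbalanced within arms. The wake-up is common to active and sham, so it adds slight noise or compression.
- That the trial ignores the MEQ as a factor. The secondary objective under Aim 1 covers self-reported preference and its possible interaction with tDCS, and Protocol 9.1 lists the MEQ. The gap is confined to SAP 1.c.

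**Conclusion.** The point holds in a limited form. Unless a night rule is added, the 1.c moderator draws on at least two post-stimulation nights for every completer, and on the 7-day schedule the plan's own minimum makes this unavoidable. The night before the AM visit is always in the record. A measure free of both problems is already planned for everyone, but 1.c does not use it as a moderator.

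The percentages count nights; they do not measure bias. The bias from post-stimulation nights cannot be sized from the documents, and that from the AM-visit night is modest under the assumed wake-time values. This is a cheap improvement to the interpretability of 1.c. It is not evidence that 1.c would give a wrong answer.

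**What to change.** In SAP 1.c:

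1. Pre-specify the same model with baseline MEQ score as a parallel moderator, report it beside the accelerometry model, and state that it carries the most weight if the two differ.
2. Derive the main accelerometry variables without the night before the AM visit. This leaves 7 − 1 = 6 nights on the 7-day schedule, so state that the 7-day minimum refers to the recording and not to the nights used.
3. Report a sensitivity run on nights before the first tDCS session only, as description. It should have no veto over the conclusion, because so few nights measure habitual timing poorly.

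**Cost.** Each person loses one night from the main variables. The sensitivity run may rest on two nights, or on one for an AM-first participant with tDCS on day 2 if the night before the AM visit is dropped there too. 1.c is run for two tasks, each with and without baseline adjustment, so the two added versions mean 2 × 2 × 2 = 8 extra fits. No new data are needed. Protocol 9.2.1 keeps the stimulation codes sealed while the team can see the other data, so the rule can be fixed without knowledge of treatment effects if the codes have not yet been broken.
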